10.7. Appendix 7: Abbreviations and Definitions

Term	Definition
abuse	Use of a study intervention for recreational purposes or to maintain an addiction or dependence
AE	adverse event
ALP	alkaline phosphatase
ALT	alanine aminotransferase
AST	aspartate aminotransferase
AWARD	Assessment of Weekly AdministRation of LY2189265 in Diabetes
BG	blood glucose
BMI	body mass index
CDSCO	Central Drugs Standard Control Organisation
CFR	Code of Federal Regulations
CI	confidence interval
CKD-EPI	chronic kidney disease-epidemiology
complaint	A complaint is any written, electronic, or oral communication that alleges deficiencies related to the identity, quality, purity, durability, reliability, safety or effectiveness, or performance of a drug or drug delivery system.
compliance	Adherence to all study-related, good clinical practice (GCP), and applicable regulatory requirements.
COVID-19	coronavirus disease 2019
CRF	case report form
	A printed, optical, or electronic document designed to record all of the protocol-required information to be reported to the Sponsor for each trial participant.
CRO	contract research organization
CTA	clinical trial agreement
Data monitoring committee	A data monitoring committee, or data monitoring board is a group of independent scientists who are appointed to monitor the safety and scientific integrity of a human research intervention, and to make recommendations to the Sponsor regarding the stopping of a study for efficacy, or for harms, or for futility. The composition of the committee is dependent upon the scientific skills and knowledge required for monitoring the particular study.

DBP	diastolic blood pressure
ECG	electrocardiogram
eCRF	electronic case report form
EDC	electronic data capture system
eGFR	estimated glomerular filtration rate
enroll	The act of assigning a participant to a treatment. Participants who are enrolled in the study are those who have been assigned to a treatment.
enter	Participants entered into a study are those who sign the informed consent form directly or through their legally acceptable representatives.
FAS	full analysis set
FBG	fasting blood glucose
GCP	good clinical practice
GI	gastrointestinal
GLP-1 RA	glucagon-like peptide-1 receptor agonist
HbA1c	hemoglobin A1c
IB	investigator's brochure
ICF	informed consent form
ICH	International Council for Harmonisation
IEC	independent ethics committee
IMP	investigational medicinal product (see also "investigational product") A medicinal product which is being tested or used as a reference, including as a placebo, in a clinical trial.
informed consent	A process by which a participant voluntarily confirms their willingness to participate in a particular study, after having been informed of all aspects of the study that are relevant to the participant's decision to participate. Informed consent is documented by means of a written, signed, and dated ICF.
interim analysis	An interim analysis is an analysis of clinical study data, separated into treatment groups, that is conducted before the final reporting database is created/locked.

IP	investigational product A pharmaceutical form of an active ingredient or placebo being tested or used as a reference in a clinical trial, including products already on the market when used or assembled (formulated or packaged) in a way different from the authorized form, or marketed products used for an unauthorized indication, or marketed products used to gain further information about the authorized form. See also “IMP.”
IRB	institutional review board
LOCF	last observation carried forward
medication error	Errors in the prescribing, dispensing, or administration of a study intervention, regardless of whether or not the medication is administered to the participant or the error leads to an AE. Medication error generally involve a failure to uphold 1 or more of the 5 “rights” of medication use: the right participant, the right drug, the right dose, the right route, and at the right time. In addition to the core 5 rights, the following may also represent medication errors:
	
 • dose omission associated with an AE or a PC • dispensing or use of expired medication • use of medication past the recommended in-use date • dispensing or use of an improperly stored medication • use of an adulterated dosage form or administration technique inconsistent with the medication's labeling (for example, summary of product characteristics, IB, local label, and protocol), or • shared use of cartridges, prefilled pens, or both.
misuse	Use of a study intervention for self-treatment that either is inconsistent with the prescribed dosing regimen, indication, or both, or is obtained without a prescription
MMRM	mixed model for repeated measures
OHAs	oral hypoglycemic agents

TLFs	Tables, data listings and figures
WHO	World Health Organization
WHO-DD	WHO Drug Dictionary

1. Overview

1.1 Introduction

This document describes the rules and conventions to be used in the presentation and analysis of a 24-week multicentre, open-label, single-arm study to evaluate safety in patients with type 2 diabetes mellitus in India treated with dulaglutide.

This statistical analysis plan (SAP) is based on protocol H9X-IN-GBGR, 1.0, dated 02-Jun-22.

2. Trial objectives

The following objectives are those stated in the protocol.

2.1 Primary objectives

- Assess the safety profile of 1.5 and 0.75 mg dulaglutide in patients with T2DM in India

2.2 Secondary objectives

- Change in HbA1c for pooled doses of dulaglutide

2.3 Exploratory objectives

- Change in body weight
- Change in FBG
- Change in vital signs

3. Endpoints

3.1 Primary endpoints

- Incidence of AEs (deaths, SAEs, TEAEs, and hypoglycemia, including severe hypoglycemia)
- Proportion of patients reporting AEs and SAEs between baseline and Week 24
- Incidence of GI AEs

3.2 Secondary endpoints

- Mean change in HbA1c from baseline to Week 24

3.3 Exploratory endpoints

- Mean change in body weight from baseline to Week 24
- Mean change in FBG from baseline to Week 24
- Mean change in systolic blood pressure, diastolic blood pressure, and pulse rate from baseline to Week 24

4. Trial design

4.1 Design overview

This is a Phase 4, single-arm study to study the safety of dulaglutide in patients with T2DM in India who are on stable doses of oral antihyperglycemic medications with or without stable doses of basal or premix insulin for the last 3 months prior to screening.

The study consists of below visit:

- Screening visit
- 2-week lead-in period
- 24-week treatment period, and
- Safety follow-up visit.

4.2 Schedule of events

Refer to the protocol section 1.3 for the schedule of activities.

5. Changes/deviations from the planned analysis

The statistical analysis/methods as described in the protocol were adopted. There are no changes to the planned analyses. Any deviation from original statistical analysis plan will be described and justified in the final clinical study report.

6. Analysis populations

Agreement and authorization of participants included/excluded from each analysis population will be reached prior to final database hard lock. Sponsor will review/supply a list of all participants to be excluded from the relevant analysis populations, including the reason(s) for exclusion from the analysis populations.

6.1 Enrolled Analysis Set (ENRL)

All participants who sign informed consent form and are screen positive.

6.2 Full Analysis Set (FAS)

All patients who received at least 1 dose of study treatment and have at least 1 measurement of HbA1c after study treatment.

6.3 Per-Protocol Analysis Set (PP)

All patients in the FAS who meet the following criteria

- Have no important (major) protocol deviations that could impact the assessment of the primary objective
- are at least 80% compliant with the study drug in terms of dose taken
- have no instance of deviation from persistence with study drug in terms of no more than the 15 days gap between 2 consecutive doses
- complete the treatment phase (24 weeks) for the primary endpoint

6.4 Safety Analysis Set (SAF)

All patients who received at least 1 dose of study treatment.

7. General considerations

7.1 Visit and date conventions

Visit day will be calculated from the reference start date which will be used to present start/stop day of assessments and events. The *reference start date* is defined as the date of first study treatment administration. The following conventions will be used for visit references:

- Visit day = date of Visit – reference start date
- Visit week = $\frac{\text{visit day}}{7}$, rounding up to next whole number
- If event date < reference start date then event day= (date of event - reference start date), Otherwise if event date is on or after reference start date then event day= (date of event - reference start date) +1

No visit windowing (i.e., remapping of visits based on visit windows) will be performed for this trial. The assigned nominal visit will be used for by-visit summaries. Unscheduled measurements will not be included in by-visit summaries.

7.2 Baseline

Baseline is defined as the last non-missing observation made prior to the first treatment administration.

7.3 Stratifications

In general, the treatment will be presented as overall strata (i.e., Dulaglutide treatment group). However if more than 20% of the subjects undergo dose modification/downgrade or receive only 0.75 mg dose during the trial, then separate strata will be presented apart from overall: subjects with 1.5 mg only, subjects with any dose modification (at least one dose of 1.5 mg and at least 1 dose of 0.75 mg) and subjects with 0.75 mg only if they constitute more than 20% of the enrolled population. If 0.75 mg only group constitutes less than or equal to 20% of enrolled population then it can be clubbed together with the dose modified group.

Note: The dose modification may not be applicable for those who start on 0.75 mg and upgrade to 1.5 mg.

Subgroup analysis will be done on the primary, secondary, and exploratory data based on the below stratification:

- age (<65 year and \geq 65 year)
- HbA1c (<8.5 and \geq 8.5)
- Sex (Female and male)
- BMI category (<27 kg/m²) and \geq 27 kg/m²)

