6.1. Study Intervention(s) Administered

This table lists the intervention used in this clinical study.

Intervention Name	Dulaglutide
Dosage Levels	0.75 or 1.5 mg
Route of Administration	Subcutaneous injection
Frequency of Administration	Once weekly

[figure not shown]
The following circumstances are permitted:

[figure not shown]
1. Treatment will be started with dulaglutide 1.5 mg as combination therapy or dulaglutide 0.75 mg as combination therapy or monotherapy. For patients who report GI AEs after starting treatment with 1.5 mg dulaglutide, the investigator may reduce the dose to 0.75 mg based on symptoms reported by patients. Treatment will be continued with 0.75 mg for 2 to 3 weeks. Thereafter, the 1.5-mg dose will be reintroduced.
2. As per common practice in India, treatment may be started with 0.75 mg dulaglutide as combination therapy in select cases. The dose may be up titrated to 1.5 mg after a period of 2 to 4 weeks in consultation with the medical monitor.

IP dispensing scenarios

[figure not shown]
IP dispensing will be done at Visit 2 for first 3 months of therapy and again at Visit 5 for next 3 months of therapy.

The various IP dispensing scenarios are shown in [Figure 6.1](#).

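### The primary objective covers 1.5 and 0.75 mg, but SAP 7.3 does not guarantee any summary of a primary safety endpoint at 0.75 mg, and its dose strata can understate GI events on 1.5 mg

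*SAP*

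**What the plan says.** The primary objective (SAP 2.1, matching Protocol 3) is to "Assess the safety profile of 1.5 and 0.75 mg dulaglutide in patients with T2DM in India". The secondary objective (SAP 2.2) is worded differently: "Change in HbA1c for pooled doses of dulaglutide".

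SAP 7.3 sets the presentation for all tables:

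- The default is a single overall dulaglutide group: "In general, the treatment will be presented as overall strata (i.e., Dulaglutide treatment group").
- The trigger for dose strata is: "if more than 20% of the subjects undergo dose modification/downgrade or receive only 0.75 mg dose during the trial, then separate strata will be presented".
- Once triggered, the strata are 1.5 mg only, any dose modification (at least one dose of each strength), and "subjects with 0.75 mg only if they constitute more than 20% of the enrolled population".
- Otherwise: "If 0.75 mg only group constitutes less than or equal to 20% of enrolled population then it can be clubbed together" with the dose-modified patients.
- A note adds that dose modification may not apply to patients who start on 0.75 mg and move up.

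The analysis sections (for example SAP 15.2.1, 18.1.2, 18.2.2 and 18.3.2) refer back to 7.3 but name only dose modification above 20% as the trigger. The same SAP repeats the primary analyses by age, HbA1c, sex and BMI category, with no size condition.

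On dosing, Protocol 6.1 and 6.5 allow a reduction to 0.75 mg for GI AEs on 1.5 mg, for 2 to 3 weeks, and then: "Thereafter, the 1.5-mg dose will be reintroduced". Patients who start on 0.75 mg in combination may be moved to 1.5 mg after 2 to 4 weeks.

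**The concern.** The two objectives sit in one table and only one of them is pooled, so the natural reading is that the primary objective asks for safety at each dose. The plan makes that answer conditional on how many patients happen to stay on 0.75 mg. It applies no such condition to four subgroup factors that the objective does not mention.

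There is a second difficulty when the strata are shown. Patients are classified by the doses they received over the whole trial, and one route from 1.5 mg only to dose modification is a GI AE on 1.5 mg. GI AEs are a named primary endpoint, so group membership depends partly on the outcome being summarised. The SAP 18.3.2 hazard ratio for dose, with 1.5 mg as reference, has the same weakness.

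At stake is whether a reader of the report could find a tabulated safety result for 0.75 mg, and could take the 1.5-mg-only column at face value.

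**Working it through.** **Plan's own figures (Protocol 9.6).** 250 × (1 − 0.20) = 200 treated; 200 × (1 − 0.20) = 160 completers. Both reproduce. Neither figure is split by dose.

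**What the 20% rule requires.** Taking 200 as the enrolled number, 20% × 200 = 40. A guaranteed 0.75-mg-only stratum therefore needs at least 41 patients who never received 1.5 mg; up to 40 can be merged.

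**Chance of reaching 41.** This is P(X ≥ 41) for X ~ Binomial(200, p), where p is the true share of 0.75-mg-only patients. The documents give no value for p, so these are assumptions across a range:

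| Assumed p | P(X ≥ 41) |
|---|---|
| 10% | <0.01% |
| 15% | 2.2% |
| 18% | 20% |
| 20% | 46% |
| 22% | 72% |
| 25% | 94% |

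Put another way, if 30% of patients start on 0.75 mg, more than 0.20/0.30 = 67% of them must never move up. If 50% start on it, more than 0.20/0.50 = 40% must stay. If 20% or fewer start on it, the rule cannot be met.

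**Precision of a small 0.75 mg column.** The method is Clopper-Pearson, two-sided 95%, as in SAP 18.2.2. With zero events the upper limit is 1 − 0.025^(1/n):

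| n | Upper limit, zero events | 95% CI if 20% have the event |
|---|---|---|
| 10 | 30.8% | 2.5–55.6% |
| 20 | 16.8% | 5.7–43.7% |
| 40 | 8.8% | 9.1–35.6% |
| 200 | 1.8% | 14.7–26.2% |

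**Selection out of the 1.5-mg-only group.** Among patients who start on 1.5 mg, let g be the proportion with a GI AE and d the proportion of those who are then reduced. If no one is reduced for another reason, GI incidence in those remaining as 1.5 mg only is g(1 − d)/(1 − gd). This is below g whenever d > 0 and 0 < g < 1, because 1 − d < 1 − gd. The direction is therefore known; the size depends on g and d, which the documents do not give.

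**The case against.** The best defence is that the objective can be read as covering the regimen as used. The primary endpoints are not dose-specific, Protocol 9.4.2 speaks of patients given either dose, SAP 23.8 labels treatment as one entity, and the study is single-arm with no hypotheses. That reading is possible, but the explicit pooling in the secondary objective alone tells against it. If it is what the sponsor means, the objective should say so.

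A minimum size before showing a stratum is also an ordinary presentation choice. That carries less weight here, because the trial is descriptive and the SAP runs four other splits with no minimum.

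Several stronger readings are tempting, and the documents do not support them:

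- *The 0.75 mg question will probably go unanswered.* The dosing paths lean towards 1.5 mg, but up-titration is optional, 0.75 mg may be a starting dose, and no share is projected. The probabilities above run from near zero to 94%.
- *The SAP merges the groups and leaves the report with no 0.75 mg data.* Merging is permitted, not required. The count of 0.75-mg-only patients (SAP 10.1), a per-subject dose plot (12.2) and by-subject AE listings (15.2) are planned regardless. What is not guaranteed is a summary. The separate output templates are not available, so this rests on the SAP text.
- *Pooling materially dilutes the 1.5 mg rate.* Neither patient-time by dose nor relative AE rates are given. If 20% of patients were reduced for 3 of 24 weeks, 0.20 × 3/24 = 2.5% of patient-time would be on 0.75 mg. Even an assumed half rate there would lower the pooled rate by only 1.25%.
- *Assigning events to the dose at onset settles the matter.* Protocol 4.2 says GI events come early and subside over 2 to 4 weeks. In mixed-dose patients, time on 0.75 mg falls in those first weeks or just after a GI event on 1.5 mg. Such rates mix dose with time since initiation and with intolerance, so they can only supplement the dose-pattern table.

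**Conclusion.** The concern holds as a gap between the primary objective and the guaranteed output. Under SAP 7.3 up to 40 of 200 patients could have received only 0.75 mg without any primary safety endpoint being tabulated for them. This rests on 200 enrolled, all treated, and on reading the primary objective as dose-specific. The likelihood turns on an unknown share.

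Where strata are shown, the 1.5-mg-only column can understate GI incidence, by an amount that cannot be computed from the documents. Two wording problems add to the uncertainty: the analysis sections state a narrower trigger than 7.3, and the 7.3 note leaves unclear which stratum holds patients who start on 0.75 mg and move up, although by definition they have received both strengths.

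This is a worthwhile and cheap correction to the SAP. It does not undermine the overall safety description.

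**What to change.** In SAP 7.3, 15.2 and 18:

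1. Remove the 20% condition for the primary safety tables. Always show 1.5 mg only, 0.75 mg only and both doses beside the overall column, descriptively, with exact confidence intervals for the proportions.
2. State which stratum holds patients who start on 0.75 mg and move to 1.5 mg, and use one definition throughout.
3. Footnote that reduction after a GI AE takes patients out of the 1.5-mg-only column.
4. Add one supplementary table of TEAEs, SAEs, GI AEs and hypoglycaemia by the dose last injected before onset, with patient-time at each dose as denominator. Footnote it for carry-over after a switch and for confounding with time since initiation and prior GI intolerance.
5. Make no between-dose test. SAP 18.3.2 adds a dose hazard ratio and p-value whenever dose strata are analysed, so say that showing the strata does not call for it.

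If the sponsor does mean pooled doses, the alternative is to say so in the primary objective.

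The cost is SAP wording and some programming on injection and AE onset dates already collected; no dosing rule changes. The downside is small cells with wide intervals, as tabulated above, which a descriptive study can carry if they are labelled as such.

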9.4. Statistical Analyses

9.4.1. General Considerations

Statistical analysis of this study will be the responsibility of Lilly or its designee. Any change to the data analysis methods described in the protocol will require an amendment only if it changes a principal feature of the protocol. Any other change to the data analysis methods described in the protocol and the justification for making the change will be described in the CSR. Additional exploratory analyses of the data will be conducted as deemed appropriate.

All data will be entered, verified, and archived by a CRO external to Lilly and/or at Lilly. Data listings, summaries, and analyses will be performed by a CRO under the guidance and approval of statisticians at Lilly.

Summary statistics will be provided for the observed value, and change from baseline will be summarized.

Unless otherwise specified, listings will include all enrolled patients. Efficacy analyses will be conducted using the FAS.

Similarly, the exploratory measures (change in body weight from baseline and change in FBG from baseline) will be evaluated in the FAS population.

Also, safety analyses will be conducted on the safety population. The exploratory measures of vital signs (change in SBP, DBP, and pulse rate from baseline) will be analyzed using the safety population).

Unless otherwise specified, testing effect of dulaglutide on change from baseline will be conducted at a 2-sided alpha level of 0.05, and CIs will be calculated at 95%, 2-sided.

For continuous measures, summary statistics will include number of patients, mean, SD, median, minimum, maximum, and interquartile ranges for both the actual and the change from baseline measurements. Number of missing values will be specified along with this information.

For categorical measures, summary statistics will include sample size, frequency, and percentages. Number of missing values will be specified along with this information.

No multiplicity adjustment will be done in this study.

Change from baseline will only be calculated for patients with both baseline and post baseline values as:

$$\text{Change from baseline} = \text{postbaseline value} - \text{baseline value}.$$

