9.4.6. Other Analyses

A detailed description of subject disposition will be provided at the end of the study.

Concomitant medications, including previous therapy for diabetes, will be summarized by different categories and concomitant medication treatment group using the safety population. All concomitant therapies that were originally mapped using the WHO Drug Dictionary in the ClinTrial database will be further classified using Anatomical Therapeutic Chemical codes for reporting purposes.

Subject compliance with study medication will be assessed at each visit of the treatment period and overall.

Subgroup analysis will be done on the primary, secondary, and exploratory data based on the stratification of age (<65 and \geq 65), HbA1c (<8.5 and \geq 8.5), sex, and BMI category (<27 and \geq 27) if needed. Details will be provided in SAP.

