7.4 Statistical tests

Unless otherwise specified, testing effect of dulaglutide on change from baseline will be conducted at a 2-sided alpha level of 0.05, and CIs will be calculated at 95%, 2-sided.

The mixed model for repeated measures method, Negative binomial models, and Cox proportional hazard models techniques will be used.

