19.1.2 Analyses

Population: FAS and PP

Stratification: Table: Add the strata as needed in case subjects with dose modification exceeding 20% based on enrolled population as per section 7.3:

- a. Subjects on 1.5 mg only
- b. Subjects on 0.75 mg only
- c. Subjects with any dose modification*

* Subjects who have received at least one dose of 1.5 mg and at least one dose of 0.75 mg

Statistics: The mean change in HbA1c level from baseline to Weeks 12 and 24 for all available data including post-rescue medication values will be analysed using descriptive statistics (mean, median, SD, SE, minimum, maximum, and number with missing values). In addition, for the actual value and change from baseline, a descriptive analysis using LOCF will be performed, using the baseline or 12-week value, if the 24-week value is missing or occurred after use of rescue medication.

For subjects requiring rescue medication, HbA1c values recorded after the first administration of rescue medication will not be

considered for analysis, and these values will be considered as missing.

Note: Rescue medications will be identified by the medical team.

The MMRM will be used for analysis of the change in HbA1c level from baseline to Weeks 12 and 24. An unstructured covariance structure will be used to model the within-patient variability and implicitly adjust for missing data. If this analysis fails to converge, the following covariance structures will be tested in order.

1. Toeplitz with heterogeneity
2. Autoregressive with heterogeneity, by visit
3. Compound symmetry with heterogeneous variances, by visit
4. Toeplitz
5. Autoregressive
6. Compound symmetry without heterogeneous variances, by visit

From the above covariance structures, the first covariance structure that converges will be used. The Kenward-Roger approximation will be used to estimate denominator degrees of freedom. Significance tests will be based on least-squares mean using Type III sum of squares.

The MMRM for each of the endpoints will include the respective baseline score and any covariates. Baseline insulin level, insulin regimen and insulin use(yes/no) will be included as covariates in the model if convergence is met. If convergence is not met with baseline insulin level and insulin regimen as covariates, then only insulin use(yes/no) will be used.

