If convergence is not met in the MMRM, the change in HbA1c level from baseline to Week 24 will be analysed using the general linear model. The general linear model will evaluate the change from baseline in HbA1c level as the dependent variable and the

baseline value of HbA1c as covariate. The LOCF method of missing value imputation will be used.

Additionally, all the analysis will be repeated for the below mentioned subgroups:

- age (<65 year and \geq 65 year)
- HbA1c (<8.5 and \geq 8.5)
- Sex (Female and male)
- BMI category (<27 kg/m²) and \geq 27 kg/m²)

Forest plot of Mean change from baseline of HbA1c for overall and subgroup will be presented. Line plot will be plotted to show the trend of HbA1c lowering. Mean change values will be used by timepoint for plotting.

20. Exploratory endpoint**20.1 Mean change in body weight from baseline to Week 24****20.1.1 Variables and derivations**

Variables:

- Weight (in Kgs)

Derivations:

- Weight (in Kgs) results between visit baseline visit 2 (week 0) and visit 8 (week 24) will be used.

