20.1.2 Analyses

Population: FAS and PP

Stratification: Table: Add the strata as needed in case subjects with dose modification exceeding 20% based on enrolled population:

- Subjects on 1.5 mg only
- Subjects on 0.75 mg only
- Subjects with any dose modification*

* Subjects who have received at least one dose of 1.5 mg and at least one dose of 0.75 mg

Statistics: The actual values and change from baseline will be summarized by descriptive statistics (n, missing values, mean, median, SD, SE, minimum, and maximum) by visit. No multiplicity adjustment will be done.

The analysis of Mean change in weight at 24 weeks will use the MMRM. Missing data will be assumed missing at random and will be accommodated by the MMRM. The MMRM using restricted maximum likelihood will be done for analyses (note: statistical comparison will not be conducted) during the entire study period. An unstructured covariance structure will be used to model the within-patient variability and implicitly adjust for missing data. If

this analysis fails to converge, the following covariance structures will be tested in order.

1. Toeplitz with heterogeneity
2. Autoregressive with heterogeneity, by visit
3. Compound symmetry with heterogeneous variances, by visit
4. Toeplitz
5. Autoregressive
6. Compound symmetry without heterogeneous variances, by visit

The first covariance structure that converges will be used. The Kenward-Roger approximation will be used to estimate denominator degrees of freedom. Significance tests will be based on least-squares mean using Type III sum of squares.

If none of the models converge then an analysis of covariance using LOCF imputation with similar terms as in the MMRM (except no terms that include visit) will be used in its place. The model will evaluate the change from baseline in weight as the dependent variable and the baseline value of weight as covariate.

The MMRM for each of the endpoints will include the respective baseline score and any covariate. Baseline HbA1c and baseline insulin use will be included as covariate in the model if convergence is met. If convergence is not met with baseline insulin level and insulin regimen as covariates, then only insulin use(yes/no) will be used for insulin usage.

Additionally, all the analysis will be repeated for the below mentioned subgroups:

- age (<65 year and \geq 65 year)
- HbA1c (<8.5 and \geq 8.5)
- Sex (Female and male)
- BMI category (<27 kg/m²) and \geq 27 kg/m²)

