Additionally, all the analysis will be repeated for the below mentioned subgroups:

- age (<65 year and \geq 65 year)
- HbA1c (<8.5 and \geq 8.5)

- Sex (Female and male)
- BMI category (<27 kg/m²) and \geq 27 kg/m²)

21. Other assessments

The listings will be presented for 12-Lead ECG data at screening using SAF population.

The Physical examination assessment will be presented in data listings and summarised as number and percentage (n and %) using SAF population. Physical examination data will be classified as normal and abnormal.

22. Revision history

Version	Date	Change
1.0	19-Dec-2022	Original Document
2.0	19-May-2023	
1. Updated Enroll Population Definition2. Added plots for the HbA1c analysis3. Updated primary and secondary analysis text for the 95% CI presentation in mock shells.4. Added plots vital sign parameters.

23. Appendix 1: Programming Conventions for Tables, Data Listings and Figures (TLFs)

Programs will be developed and maintained and output will be verified in accordance with current risk-based quality control procedures. Tables, figures, and listings will be produced with validated software. The production environment for statistical analysis consists of statistical analysis software; for example, the SAS System version 9.4 or later.

All percentages (%) for a specific summary are calculated using the total number of subjects included in the relevant analysis population as the denominator, unless otherwise specified.

Data listings will be based on all subjects, unless otherwise specified.

In general, if we have no response or record for respective parameter in data (i.e., n=0) then while presenting statistics in table only n will be presented as "0" and other statistics will be left blank. In case we have only one response or record for respective parameter (i.e., n=1) in data then statistic SD in table will be left blank.

By default, for continuous measures, summary statistics will include, unless otherwise specified:

- n
- Mean
- Median
- Maximum
- Minimum
- Standard error
- SD
- Frequency of Missing Values.

For categorical measures, summary statistics will include, unless otherwise specified:

- Frequency of non-missing values
- Percentage, and
- Frequency of Missing Values.

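### The HbA1c subgroup plan tests change at 0.05 within each of eight levels but never estimates whether the levels differ, and no subgroup result is labelled exploratory

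*SAP*

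**What the plan says.** SAP 7.3 names four two-level factors: age at 65 years, HbA1c at 8.5, sex, and BMI at 27 kg/m². It states: "Subgroup analysis will be done on the primary, secondary, and exploratory data based on the below stratification". Each endpoint section (18.1.2, 18.2.2, 18.3.2, 19.1.2, 20.1.2, 20.2.2 and 20.3.2) carries the sentence "Additionally, all the analysis will be repeated for the below mentioned subgroups". The tables in SAP sections 10 to 17 do not.

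The testing rules differ by endpoint:

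- **Default (SAP 7.4).** Unless otherwise specified, "testing effect of dulaglutide on change from baseline will be conducted at a 2-sided alpha level of 0.05".
- **HbA1c (SAP 19.1.2).** "Significance tests will be based on least-squares mean using Type III sum of squares". The section also promises a display: "Forest plot of Mean change from baseline of HbA1c for overall and subgroup will be presented".
- **Weight, FBG, SBP, DBP and pulse (SAP 20.1.2, 20.2.2, 20.3.2).** Each section carries the remark "note: statistical comparison will not be conducted", and each also has the least-squares-mean testing sentence used for HbA1c.
- **Primary safety endpoints (SAP 18).** Incidences, rates, exact intervals for proportions and time-to-event models, with no test of change from baseline.

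No model in SAP 19 or 20 lists a subgroup term, a subgroup-by-visit term or a between-level difference. On multiplicity, Protocol 9.4.1 states: "No multiplicity adjustment will be done in this study".

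**The concern.** A subgroup analysis asks whether the levels differ. Testing each level against zero answers another question, namely whether that level changed. When one level reaches p < 0.05 and the other does not, the pattern looks like a difference. It can arise from unequal level sizes, or from chance when each level has moderate power, even if the true change is identical in both.

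HbA1c is where this applies most clearly, because its section contains the testing sentence without the no-comparison remark. What is at stake is how the subgroup results are read. No confirmatory claim depends on them.

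**Working it through.** **Inputs from the documents.** Two-sided alpha of 0.05 (SAP 7.4). Four factors × 2 levels = 8 levels (SAP 7.3). Protocol 9.6 gives 250 screened, 20% screen failure and 20% dropout. Its figures reproduce: 250 × 0.80 = 200 treated, and 200 × 0.80 = 160 completers.

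**Assumptions.** The documents give no SD, expected change or subgroup shares. The true mean change d is therefore varied in SD units and is the same for every patient. The smaller level is set at 50%, 20% or 10% of 160.

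**Step 1: one factor.** By normal approximation, a level of size n is significant with probability

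p(n, d) = Φ(d√n − 1.96) + Φ(−d√n − 1.96).

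Treating the two levels as independent, the chance that exactly one is significant is p₁(1 − p₂) + p₂(1 − p₁).

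- 80/80 at d = 0.2: d√n = 1.789 and p = 0.432, so 2 × 0.432 × 0.568 = 0.491.
- 32/128 at d = 0.3: p₁ = 0.396 and p₂ = 0.924, so 0.396 × 0.076 + 0.924 × 0.604 = 0.588.

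Chance that exactly one level is significant although both have the same true change:

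| Split | d = 0.2 | d = 0.3 | d = 0.5 | d = 0.67 |
|---|---|---|---|---|
| 80/80 | 49% | 36% | 1% | about 0% |
| 32/128 | 57% | 59% | 19% | 3% |
| 16/144 | 63% | 75% | 48% | 24% |

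**Step 2: at least one of four factors.** Simulated with t tests, 160 patients, 20% aged 65 or over, the other factors 50:50, and all factors independent:

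| True change (SD) | 0.1 | 0.2 | 0.3 | 0.5 | 1.0 |
|---|---|---|---|---|---|
| At least one factor significant in one level only | 48% | 82% | 79% | 24% | 0% |

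Independent repeats agree to within about two percentage points. With all four factors split 50:50, the figures are 80% at 0.2 SD, 64% at 0.3 SD and under 0.1% at 0.67 SD.

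**Step 3: a direct contrast.** A between-level test has a 5% false-positive rate per factor whatever the overall change. For four independent contrasts, 1 − 0.95⁴ = 18.5%; simulation gives 17% to 20%. Contrasts therefore need an exploratory label too.

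**Step 4: what a contrast can detect.** The difference detectable with 80% power is (1.96 + 0.842) × √(1/n₁ + 1/n₂): 0.44 SD for 80/80, 0.55 SD for 32/128 and 0.74 SD for 16/144. Only large differences between levels could be established.

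**The case against.** The best defence is that this is a descriptive single-arm safety study. Protocol 9.1 gives no hypotheses, and the absence of multiplicity adjustment is stated openly. The SAP plans 95% CIs and an HbA1c forest plot, so a reader can compare estimates and need not rely on significance. The table templates are in a separate document, and the SAP does not say that HbA1c p-values by level will be printed. If the HbA1c change is large and the levels balanced, discordance is close to nil, whereas four unadjusted contrasts would give a false difference in nearly one trial in five.

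Most of this stands, and it limits the size of the point. It does not remove the gap: two intervals side by side do not give the interval for their difference. The contrast's error rate also stays the same whatever the effect size and level size, while the error from comparing significance does not.

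Three stronger readings are tempting, and the documents do not support them:

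- **Every analysis tests change at 0.05 in each level.** The repeat sentence is confined to SAP 18 to 20, the primary endpoints have no such test, and the five exploratory variables carry contradictory instructions.
- **The SAP breaches the protocol by making subgroups mandatory.** Protocol 9.4.6 does make them conditional, but its wording is "if needed. Details will be provided in SAP", which leaves the specification to the SAP.
- **False subgroup effects are to be expected for HbA1c.** That holds only for a modest change or a small level, and the documents state neither.

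**Conclusion.** The point holds in a limited form. SAP 18 to 20 repeat the endpoint analyses in eight levels with no between-level contrast and no exploratory label, and for HbA1c this implies a 0.05 test within each level. The chance of a misleading pattern in at least one factor runs from about 80% at 0.2 to 0.3 SD, through about 25% at 0.5 SD, to 0% at 1 SD. These figures assume 160 completers, 20% aged 65 or over, even splits elsewhere, independent factors and one common true change. For HbA1c the practical risk lies mainly in a small level: at 0.67 SD it is about 0% for an 80/80 split and 24% for 16/144.

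For weight, FBG, SBP, DBP and pulse, the SAP must first settle whether any test is intended. The change is a cheap improvement and should be made.

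**What to change.** 1. **SAP 19.1.2.** For age, sex and BMI, fit one MMRM per factor in the FAS with subgroup and subgroup-by-visit terms. Report the Week 24 estimate and 95% CI per level without within-level p-values. Show the between-level difference with its 95% CI on the forest plot.
2. **HbA1c split at 8.5.** Do not add the category to a model that already has continuous baseline HbA1c. Either use a baseline-by-visit term or show level estimates only. Note that this split is open to regression to the mean.
3. **SAP 7.3.** State that subgroup results are exploratory and unadjusted, with about an 18% to 20% chance of at least one false contrast among four. State also that, without a control arm, they describe differences in change and not in drug effect.
4. **SAP 20.1.2, 20.2.2 and 20.3.2.** Reconcile the no-comparison remark with the significance-test sentence. Keep blood pressure and pulse in the safety set, as Protocol 9.4.1 and SAP 20.3.2 specify.

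No new data are needed. The cost is SAP wording and one extra model per factor. The downsides are a residual covariance pooled across levels and wide intervals for the differences.
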